- 3. To compare self-reported adherence to TDF/FTC in the iTAB+MI-B versus iTAB arms over 48 weeks using
 - a) adherence defined as "the proportion of text-reported doses over all possible doses over 48 weeks"; missing text messages or early discontinuation of the study will be considered as no doses taken
 - b) a continuous measure of the percentage of days adherent by self reported measures (iTAB, cumulative 3 day recall, and the visual analog scale) in an "as treated" analysis for those that are retained on study
- c) stratified analysis of 3a and 3b outcomes within male-assigned at birth and female-assigned at birth groups
- 4. To compare study retention between arms, defined as the proportion of participants that complete all study visits regardless of whether they were on drug or not
- 5. To determine factors associated with poor adherence (< 719 fmol/punch over 48 weeks) and discontinuation of TDF/FTC
 - Factors considered to be associated with poor adherence to TDF/FTC will include demographics, socioeconomic status, perception of HIV risk, ongoing substance use, intimate partner violence, low health/HIV and health systems literacy, and stigma
- 6. To determine the rate of linkage and continuation of TDF/FTC at 12 weeks after study completion between arms
- 7. To determine the rate of HIV seroconversion in TDF/FTC-using transgender / gender non-confirming individuals and compare the proportion of seroconversions over 48 weeks between arms
- 8. To measure the acquisition of other sexually transmitted infections (STIs) and compare rates of acquisition of new STIs at any site between arms
- 9. To evaluate changes in risk behavior after PrEP initiation (risk compensation) by comparing the numbers of HIV positive partners, partners of unknown HIV status, unprotected insertive and receptive anal or vaginal acts between Baseline and subsequent visits
- 10. To evaluate the safety and tolerability of daily TDF/FTC as PrEP as measured by discontinuations due to
 - a) any adverse events
 - b) serious adverse events and
 - c) grade 2 or higher adverse events

Sub-study I Primary Objective: To determine whether csHT interacts with PrEP in male-assigned at birth (MAAB) persons that would affect efficacy of PrEP, measured by intracellular TDF concentrations in DBS.

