 Results must be less than 30 days old by the time of Baseline and must be filed as a source document in the participant's chart.
- Assessment of HIV acquisition risk
- Detailed medical history including medical insurance status, and current medical and psychiatric conditions.
- Detailed medication history including cross-sex hormone therapy (csHT), if applicable, and other concomitant medications.
- Collection of height and weight
- Computer-assisted self-interview (CASI) assessments

If a subject qualifies and signs consent the window to complete the baseline assessment and start PrEP will be 30 days.

Baseline Visit (Week 0; approximately 2 hours)

Baseline may occur as soon as all eligibility criteria are confirmed. Baseline procedures include:

- Randomization, stratified by site, sex assigned at birth, and prior history of PrEP use, to either the iTAB + MI-b intervention or iTAB alone arm.
 - Study coordinators will configure a participant's iTAB account based on each individual's preferences.
- A targeted physical examination, including weight
- Laboratory evaluations
 - o Rapid HIV screening (required; cannot be substituted by an earlier rapid test)
 - 3-site (throat, rectal, urine) STI NAT screening for gonorrhea and chlamydia
 - Syphilis RPR
 - Plasma hormone levels (sub-study only)
 - CBC and liver enzymes
 - Urine β-HCG will for participants capable of being pregnant
- Sample collection for banking
 - Dried blood spot (DBS) for intracellular drug levels will be collected for participants already on PrEP at the

time of Baseline

- Whole blood, plasma, and serum
- o Urine
- Rectal swabs
- CASI assessments
- Introduction to motivational interviewing for participants randomized into the iTAB + MI-b arm.
- Medication dispensation. Participants will be provided enough medication to last until the next scheduled visit through the investigational pharmacy.
- Risk reduction and medication adherence counseling. Health educators will provide HIV transmission risk reduction counseling and detailed information about the use of PrEP, including the risks, potential adverse events and the critical importance of drug adherence.
 - Standard of care HIV risk education counseling will be provided to all participants consistent with routine practice.

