¹ Only for participants curre	ently taking	n PrFP Pai	rticinants red	uirina PrFI	P dispensation dur	ing an Interi	m visit v	vill rece	ive enou	ah PrFP

Only for participants currently taking PrEP. Participants requiring PrEP dispensation during an Interim visit will receive enough PrEP to last until the next regular study visit.

Adherence and Behavioral Assessments

We will measure adherence using the self-report daily text messages. These texts will include a personalized lead-in reminder message (e.g., "Those who are closest to you care about your health") and participants will be asked "Did you take your dose today? Reply: Y) Yes N) No P) Postpone". If 'Postpone' is selected, participants will receive a follow-up message 1 hour later asking them if they took their medication (Yes or No). Participants will also have the option of determining the word used to describe the study drug (e.g., 'med', 'dose', or other personal choice). Nonresponse or a 'No' response will be counted as not taking their dose. At each follow-up

² Participants with medication interruption greater than 14 days will require confirmation of HIV seronegative status prior to re-initiation of PrEP. Re-initiation must be achieved prior to the end of the week 36 visit.

³ Only for participants capable of becoming pregnant

⁴ Only for participants currently taking csHT. Baseline and Week 12 only.

⁵ STI screen only at week 24

⁶ Week 0 DBS collected only if participant is already taking PrEP at Baseline

⁷ Interim visit for: HIV testing if off PrEP for over 1 week and had high risk event, consider NAT or Ab/Ag; STI testing only if has symptoms (urethral discharge, genital sore); if seroconverted outside study; adverse event assessment

[†] UCSD-only sub-study evaluation. Additional specimens will be collected from anatomic site of positive GC at time of treatment. ♦ UCSD-only study extension

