The study is powered to compare the primary adherence rate between the two study arms using a two-sample, two-sided proportion test. Expected drug-level adherence based on a previous study of MSM using iTAB for PrEP for this composite endpoint (>=1246) was 33%. Assuming the adherence rate of the transgender iTAB alone group will be the same the study has 77% power to detect a difference of 16% between the iTAB+MI group and the iTAB alone group, with 150 subjects per group.

Monitoring

The study team will review all adverse events during PrEP therapy as cumulative reports in both arms combined, on monthly team calls. Adverse events will be graded using the ACTG toxicity grading scale and recorded using standard CCTG AE electronic data capture. An independent Data Safety and Monitoring Board (DSMB) will not be used for this study because the drugs are licensed for this indication and relatively non-toxic.

Statistical Analysis Plan

In general, analyses of efficacy will incorporate the modified intent-to-treat (mITT) principle, namely, all randomized participants dispensed study medication will be included in the analysis. For all secondary analyses of efficacy, no adjustments for multiple comparisons will be made and a p-value of 0.05 will be considered statistically significant. Analyses of safety will be focused on "as treated" populations.

Demographic and baseline measurement variables will be summarized via standard descriptive statistics. There will be no interim analyses for futility or efficacy conducted.

Analysis of Primary Outcome

Descriptive analysis will be performed on the primary adherence outcome via a frequency table and Fisher's exact test. Logistic regression modeling will be conducted to assess the group differences while adjusting for potential covariates.

Analysis of additional Secondary outcomes

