Descriptive analysis will be performed for all the secondary outcomes. For comparisons between the two study arms, Fisher's exact test will be used for categorical outcomes; t-test or Wilcoxon rank sum test will be used for continuous outcomes. Multivariable logistic regression model will be used to study factors associated with poor adherence. Factors will include demographics, substance use, untreated mental illness, socieconomic status, low health/HIV and system literacy, fear of disclosure and non-English language. To evaluate changes in risk behavior after initiation of PrEP, descriptive summary will be provided for the number of HIV positive/unknown status partners and any unprotected anal intercourse with an HIV positive/unknown status partner by visit (at w12, 24, 36 and 48). Wilcoxon signed rank test will be used for comparison at each follow-up visit to the baseline visit. GEE model will be used to assess the change in risk behavior over time.

Safety analysis

Safety data will be reported for all the randomized subjects while they were taking or immediately (30 days) after taking study drug (as treated analysis). Tables will summarize the number of serious adverse events, adverse events (grade 2 or higher), PrEP discontinuation due to adverse events, by study arms and overall. Fisher's exact test will be used to compare the rates between the two groups. The time to TDF/FTC discontinuation due to adverse events will be compared between groups using the log-rank test and plotted using Kaplan-Meier curves.

SUB-STUDY I DESIGN

This pharmacologic sub-study will use the main study cohort to determine the interaction of cross-sex hormone therapy (csHT) on PrEP efficacy as measured by TFV-DP and FTC-TP DBS intracellular levels, and of PrEP on csHT effectiveness as measured by quantitative hormone levels in plasma.

SUB-STUDY I PROCEDURES

Subjects will be consented for participation in the sub-study at the main study's Screening Visit.

As part of the main study, plasma and DBS samples will be collected at Baseline and every 12 weeks. A Baseline DBS sample will be collected only if the subject is already on PrEP at the time of Baseline. Detailed concomitant hormone use, including route and frequency, will be collected at every clinic visit. Daily iTab responses will be used as a self-reported adherence measure.

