integrase inhibitors, protease inhibitors or investigational antiretroviral agents) – if currently on TDF/FTC for PEP or PrEP they can switch to study provided drug but can not continue any other antiretroviral agent.

- Agents with known nephrotoxic potential:
 - aminoglycoside antibiotics (including gentamicin)
 - IV amphotericin B
 - cidofovir
 - o cisplatin
 - foscarnet
 - IV pentamidine
 - IV vancomycin
 - o oral or IV gancyclovir
 - other agents with significant nephrotoxic potential
- Drugs that slow renal excretion
 - Probenecid
- Immune system modulators
 - Systemic chemotherapeutic agents (i.e. cancer treatment medications)
 - Ongoing systemic corticosteroids (with the exception of short courses of tapering steroid doses for asthma or other self- limited condition).
 - Interleukin-2 (IL-2)
 - Interferon (alpha, beta, or gamma)
- Other agent known to have a significant interaction with TDF or FTC
- 6. Proteinuria 2+ or greater by urine dipstick
- 7. Pregnancy (if individual has a uterus)
- 8. Other condition that in the opinion of the investigator would put the participant at risk or interfere with participation, complicate interpretation of study outcome data, or otherwise interfere with achieving the study objectives.

Participation into Sub-study IV will be only be offered to a subset of 20 transgender men/gender non-conforming individuals with vaginas enrolled at the UCSD AVRC. Transgender women enrolled at the UCSD AVRC who have undergone gender reassignment surgery with neovaginas will also be offered participation, although we expect this number to be guite low.

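### Objective 9 measures change after PrEP initiation from study Baseline, but Baseline is an on-PrEP value for participants already taking PrEP, and the plan does not separate them

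*Combined protocol and SAP*

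**What the plan says.** Secondary Objective 9 (section 6, Specific Aims) is "To evaluate changes in risk behavior after PrEP initiation (risk compensation) by comparing the numbers of HIV positive partners", partners of unknown status, and "unprotected insertive and receptive anal or vaginal acts between Baseline and subsequent visits". The quantity named is change after starting PrEP. The reference point is study Baseline.

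Section 9, under the analysis of additional secondary outcomes, repeats the aim and the reference point: "Wilcoxon signed rank test will be used for comparison at each follow-up visit to the baseline visit". It adds that a "GEE model will be used to assess the change in risk behavior over time". It names no population, covariate or interaction for these analyses.

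Three other places show that some participants will not be starting PrEP at Baseline:

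- Section 10, exclusion criterion 5, on other antiretrovirals: "if currently on TDF/FTC for PEP or PrEP they can switch to study provided drug".
- Section 9, schedule of evaluations, footnote 6: "Week 0 DBS collected only if participant is already taking PrEP at Baseline".
- Section 9, Baseline Visit: "Randomization, stratified by site, sex assigned at birth, and prior history of PrEP use".

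The general rule for efficacy analyses (section 9, Statistical Analysis Plan) is that "all randomized participants dispensed study medication will be included in the analysis".

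**The concern.** Study Baseline and PrEP initiation coincide only for people who start PrEP at Baseline. Someone already on PrEP contributes the difference between two on-PrEP measurements, which says nothing direct about what happened when that person started. The plan allows for this group in sampling and, through PrEP history, in randomization, but not in the analysis of Objective 9.

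Randomization gives no protection. The comparison is within person over time and is not a contrast between arms, so balancing PrEP history across arms does not change what the pooled difference measures.

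At stake is how a null result would be read. A finding of no change in risk behaviour after starting PrEP could arise partly because some of the cohort did not start PrEP at that point.

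**Working it through.** The plan gives no sample size, effect size, standard deviation or power for Objective 9, so there is no figure to reproduce. The check compares the relevant texts and then sizes the effect under stated assumptions.

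**1. Texts side by side**

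| Element | What the plan gives | Where |
|---|---|---|
| Target | Change after PrEP initiation | Section 6, Objective 9; section 9, secondary outcomes |
| Reference value | Baseline visit | Same two places |
| Current PrEP users | May enrol and switch to study drug | Section 10, exclusion criterion 5 |
| Current users at Week 0 | Expected; blood spot taken only from them | Section 9, Baseline Visit and schedule footnote 6 |
| PrEP history | Stratifies randomization | Section 9, Baseline Visit; Randomization and Stratification |
| Restriction, adjustment or separate reporting for Objective 9 | None stated | – |
| Pre-PrEP behaviour reference for current users | None stated | – |

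The target and the reference value agree only for people not on PrEP at Baseline.

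**2. Size for a mean change**

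Let f be the share already on PrEP at Baseline, D the mean change in initiators, and d the mean change in current users.

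Pooled mean change = (1 - f) × D + f × d.

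If current users have already shifted and are stable, d = 0 and the pooled change is (1 - f) × D. Both f and d = 0 are assumptions; the documents give neither.

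| f (assumed) | Pooled change as a multiple of D |
|---|---|
| 5% | 0.95 |
| 10% | 0.90 |
| 20% | 0.80 |
| 30% | 0.70 |
| 50% | 0.50 |

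The factor holds for descriptive means, for a change in a proportion, and for a GEE with a linear mean. The plan does not state the GEE link. With a log or logit link the attenuation would not be exactly (1 - f).

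**3. What separating the groups does to power (illustration)**

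Inputs: N = 300 (section 9, Randomization and Stratification), an assumed standardized change of 0.20 in initiators, d = 0, within-group SD of change equal to 1, two-sided alpha 0.05, normal approximation.

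- Pooled: power = Φ(0.20 × (1 - f) × √300 - 1.96).
- Initiators only: power = Φ(0.20 × √(300 × (1 - f)) - 1.96).

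| f (assumed) | Pooled, N = 300 | Initiators only, n = 300(1 - f) |
|---|---|---|
| 10% | 88% | 91% (n = 270) |
| 20% | 79% | 87% (n = 240) |
| 30% | 68% | 83% (n = 210) |
| 50% | 41% | 69% (n = 150) |

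Under these assumptions the smaller group has more power because its change is not diluted.

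**4. The signed-rank test**

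This is not a test of the mean, so (1 - f) does not describe it. Its standard form drops exact zero differences, so current users who report identical counts would hardly affect it. Current users with non-zero scatter around zero do weaken it. Simulating that case with normal changes gives powers up to about 3 percentage points below those in the table, with the same pattern.

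**The case against.** Several opposing points have weight.

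- **The population is not stated.** The mITT rule is written for efficacy analyses, and risk behaviour is arguably not one. The phrase about change after initiation could be read as limiting the analysis to initiators. It is therefore too strong to say that the plan commits to pooling. What stands is that nothing excludes or separates current users, and the stated tests run on the enrolled cohort would include them.
- **The direction is not established.** A reader might infer that the analysis is necessarily biased toward no change. The documents do not support that. It requires current users to have finished changing and to stay flat for 48 weeks. They also receive the study's risk-reduction counselling, which could move their behaviour in its own right.
- **f may be small.** At 5% the pooled mean keeps 0.95 of the initiators' change. A reader might also infer that risk compensation would be hidden; at such values it would barely be diluted.
- **Not on PrEP at Baseline is not the same as a first start.** Past users who are restarting would remain in the main group. The eligibility text also covers PEP users, who do begin PrEP at entry.
- **The objective is limited anyway.** It has no hypothesis or power claim. Both arms receive PrEP, so a before-after change cannot be attributed to PrEP. Regression to the mean is possible because eligibility partly selects on past-year risk. Separating current users solves neither problem.
- **A fuller SAP is promised.** Section 9 calls its statistical text brief and gives precedence to a formal SAP to be finalized before database lock. That makes the repair easy, but nothing in the documents supplied makes it.

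**Conclusion.** The mismatch stands on the text. Objective 9 targets change after PrEP initiation, its reference is study Baseline, and participants for whom Baseline is an on-PrEP value may enrol and are expected. A change pooled over everyone would not estimate the stated quantity, whichever way current users' behaviour moves.

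The size is unknown. The range of 0.95 to 0.50 of the initiators' mean change rests on assumed values of f from 5% to 50% and on current users having already shifted and become stable. It concerns means and a linear GEE, not the signed-rank test. The power comparison further assumes a standardized change of 0.20.

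The consequence is confined to a secondary objective. The primary adherence comparison and its stated 77% power do not depend on it. The change is still worth making before database lock, because it is cheap and determines whether the result can be described as change after starting PrEP.

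**What to change.** In the SAP, for Objective 9:

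1. Define the main population, for both the signed-rank tests and the GEE, as participants not taking PrEP at Baseline. State how those on TDF/FTC for PEP at entry are classified.
2. Report current PrEP users separately, with a Baseline-PrEP-status-by-time term in the GEE fitted to the full cohort. State the GEE link.
3. Add a sensitivity analysis limited to participants with no prior PrEP history, using the existing stratification factor. This deals with past users who are restarting. The factor should not replace Baseline status in step 1, since a history of PrEP can mix past and current users.
4. Report the number already on PrEP at Baseline, so that f is known.

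The cost is SAP wording and a smaller sample in the main comparison, for example 240 rather than 300 if f were 20%. No new data collection appears necessary: PrEP status must be known to decide on the Week 0 blood spot, and a medication history is taken at screening.

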Hypothesis: Among transgender MAAB persons on csHT who report perfect adherence by iTAB in the past 34 days (ie, two intracellular half-lives) the mean intracellular tenofovir-diphosphate (TFV-DP) concentrations, as measured in DBS, will be equivalent to the levels of perfect adherence previously defined in MSM.

Sub-study I Secondary Objectives

- 1. To determine whether csHT interacts with PrEP in MAAB persons that would affect hormone effectiveness, measured by estrogen concentrations assessed at Weeks 0 and 12 of study follow-up.
 - **Hypothesis**: Among transgender MAAB persons on csHT, estrogen concentrations will not change significantly between baseline (Week 0) and Week 12 in individuals taking PrEP and receiving stable estrogen therapy (controlling for route and formulation).
- 2. To determine TFV-DP in MAAB of all adherence levels compared to not taking csHT, adjusting for confounding factors.
- 3. To determine TFV-DP in MAAB taking versus not taking antiandrogen medications (i.e., spironolactone, finasteride)
- 4. To measure the change in testosterone concentrations between baseline and Week 12 in female-assigned at birth (FAAB) taking PrEP and receiving stable testosterone therapy.
- 5. To determine emtricitabine-triphosphate (FTC-TP) concentrations (a measure of recent adherence) in TG / GNC persons of all adherence levels taking versus not taking hormones.
- 6. To determine changes in desired effects of csHT in TG / GNC persons taking PrEP as measured by the Body Image Scale (BIS).

Sub-study IV Objectives:

- 1. To determine the impact of genital STIs on CVF TFV levels.
- 2. To determine the impact of cytokine mediators of CV inflammation on CVF TFV levels.
- 3. To determine the impact of CV microbiome on CVF TFV levels.

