The primary outcome is the intracellular TFV-DP levels, as measured in DBS, which is a continuous variable. Comparison between the MAAB and the existing MSM data that will be compared using a two-sample t-test. Differences in the means between the two groups, along with the standard deviations (SD) and their 95% confidence intervals will be reported. As a secondary/sensitivity analysis, multiple regression analysis will be performed to study the association between clinical and demographic factors (age, race, ethnicity, education, socioeconomic status, sexual risk behaviors, substance use, depression, concomitant medications) and group, adjusting for baseline demographic, stratification variables, and clinical characteristics. Variables significantly associated with both group and outcome (p<0.10) will be included in a multiple regression model as covariates.

For the main secondary hypothesis, in MAAB on csHT, to determine the change between baseline and week 12 estradiol levels in individuals taking PrEP and receiving stable estrogen replacement (controlling for route, dose and formulation), we will use a paired t-test. As estradiol concentrations can be unpredictable, we will measure estradiol concentrations in individuals choosing not to initiate PrEP at the same time points. Similar to 3A, multiple regression models will be developed if there are factors that require adjustment in this model.

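### Sub-study I's estradiol hypothesis is worded as non-significance and tested with a paired t-test without a margin, so a non-significant result would meet it without showing that no relevant change occurred

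*Combined protocol and SAP*

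**What the plan says.** Section 6 (Specific Aims), Sub-study I Secondary Objective 1, reads: "To determine whether csHT interacts with PrEP in MAAB persons that would affect hormone effectiveness, measured by estrogen concentrations". The hypothesis under it is that "estrogen concentrations will not change significantly between baseline (Week 0) and Week 12 in individuals taking PrEP", restricted to people on stable estrogen therapy.

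In Section 9, the Analysis Plan under Sub-study Statistical Considerations gives this question its rank and its test: "For the main secondary hypothesis, in MAAB on csHT, to determine the change between baseline and week 12 estradiol levels". For participants "receiving stable estrogen replacement (controlling for route, dose and formulation), we will use a paired t-test".

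Two further provisions follow there. Because estradiol can be unpredictable, "we will measure estradiol concentrations in individuals choosing not to initiate PrEP at the same time points". In addition, "multiple regression models will be developed if there are factors that require adjustment in this model".

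No margin, confidence-interval criterion, SD, sample size or power is given for estradiol. The same sub-study's TFV-DP aim has all of these: a margin of 230 fmol/punch, a confidence-limit rule, an SD of 350 and 45 subjects at 80%.

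**The concern.** The null hypothesis of a paired t-test is zero mean change. Here the hypothesis the investigators hope to support is that same null, phrased in terms of significance. It is met whenever the test fails to reject. That can happen because estradiol did not change, or because there were too few pairs or too much variability to see a change. Poorer data therefore make the favourable answer easier to reach.

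The background to the sub-study shows why this matters. It reports concern among transgender women about PrEP affecting feminizing hormones, describes feared loss of hormone efficacy as a possible major barrier to PrEP, and notes that interactions with the high estrogen doses of csHT have not been studied. An unsupported statement of no interaction would be the costly error.

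**Working it through.** **1. The plan's own figure.** No sample size or power is stated for estradiol, so there is nothing to reproduce for this comparison. The only Sub-study I sample size is for TFV-DP. With SD 350, margin 230 and the stated shortfall of 100, one-sided 5% and 80% power:

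n = [350 × (1.645 + 0.842) / (230 − 100)]² = 44.8, so 45, as stated.

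The TFV-DP aim is thus set up with non-inferiority logic. The estradiol aim has no counterpart.

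**2. How often a real change would be missed.**

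Inputs from the documents:
- Upper bound on pairs: 280 MAAB × 70% on feminizing hormones = 196. This is before sub-study consent, the stable-therapy restriction, dropout and missing samples.
- Significance level: 0.05. The main-study plan says that for secondary efficacy analyses "no adjustments for multiple comparisons will be made and a p-value of 0.05 will be considered statistically significant". It does not give sidedness or name the sub-study.

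Assumptions:
- The test is two-sided and done on the log scale.
- The true fall is 20%, so the mean log change is ln(0.8) = −0.223.
- The SD of the log change is 0.5, 0.8 or 1.0.
- Smaller numbers of pairs are 40, 80 and 120.

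Formula: with non-centrality λ = (0.223/SD) × √n, the chance of missing the change is the probability that a non-central t with n − 1 degrees of freedom and non-centrality λ lies within ± the 97.5% point of t. For example, with SD 0.8 and n = 40, λ = 0.279 × 6.32 = 1.76, the critical value is 2.02, and the miss probability is 59%.

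| SD of log change | 40 pairs | 80 pairs | 120 pairs | 196 pairs |
|---|---|---|---|---|
| 0.5 | 21% | 2% | 0.2% | about 0% |
| 0.8 | 59% | 31% | 14% | 3% |
| 1.0 | 72% | 50% | 32% | 13% |

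**3. What week 0 represents.** The Baseline procedures collect DBS from participants already on PrEP, and the exclusion criteria let people on TDF/FTC switch to study drug. For them week 0 is not a pre-PrEP value. If a fraction f of the pairs were already on PrEP and any effect was already present at week 0, a true log change δ in new starters would appear in the pooled sample as (1 − f)δ. The documents do not give f. The dilution pulls the result towards no change, and an equivalence test on the pooled sample would suffer from it too.

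**4. What an equivalence rule would need (illustrative).** For two one-sided 5% tests with 80% power and a true change of zero, n = [(1.645 + 1.282)/m]², where m is the margin in SDs of the change. This gives 215 pairs at m = 0.20, 138 at 0.25, 96 at 0.30 and 35 at 0.50.

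**The case against.** **The decision rule is inferred.** The documents nowhere say that a non-significant p-value will be reported as no interaction. The objective is to determine whether there is one, and the Analysis Plan speaks of determining the change. A reader might infer a stated rule equating non-significance with no interaction; the text does not support that. What stands is narrower: the hypothesis itself is worded as non-significance, and nothing else in the plan defines when it is met.

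**The paired t-test is not the only evidence planned.** Estradiol will be measured in people who do not start PrEP, and regression may follow. However, no contrast between the groups, group size or margin is given. The main schedule of evaluations has no track for people who never start PrEP, and the regression is conditional. Neither provision supplies a criterion for absence of change. The promise of 95% confidence intervals in the Analysis Plan is attached to the TFV-DP comparison.

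**Hormone levels are not the whole of hormone effectiveness.** The Analysis Plan says satisfaction with physical traits matters more than levels, and compares Body Image Scale scores at weeks 0, 12 and 48. This stands and limits the stakes: the estradiol test is not the sole evidence of effectiveness. It is still called the main secondary hypothesis.

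**The percentages are not anchored in the documents.** This also stands. With SD 0.5 and 80 or more pairs, a 20% fall would rarely be missed.

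**A later SAP takes precedence.** Section 9 promises a SAP finalized before database lock. That is the natural place for the correction, but it does not alter the present wording of the hypothesis.

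**Conclusion.** The point holds as a matter of method. A hypothesis of no significant change, tested by a difference test without a margin or interval criterion, can be met without evidence that a relevant change is absent. That conclusion needs no assumed figures.

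Its practical size cannot be fixed from the documents. For a true 20% fall and SDs of log change between 0.5 and 1.0, the miss probability is 21% to 72% with 40 pairs and about 0% to 13% with 196. The effect size, the SDs, the log scale and every number of pairs below 196 are assumptions. A reader might take the higher percentages as this trial's risk; they only illustrate the principle.

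This is a secondary hypothesis of a sub-study. The randomized comparison and the TFV-DP primary aim of Sub-study I are unaffected. The change should be made, but it does not threaten the trial's main result.

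**What to change.** Amend the sub-study paragraph in the SAP before hormone results are examined:

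- Analyse log estradiol and report the week 12/week 0 geometric mean ratio with its 90% CI in participants not taking PrEP at Baseline. Report those already on PrEP separately.
- Conclude that there is no relevant change only if the whole 90% CI lies within a margin that the sponsor has fixed beforehand.
- If no margin is set, reword the hypothesis as estimation, report the ratio with its 95% CI, and state that a non-significant p-value will not be read as no interaction.
- Where estradiol data exist for people not on PrEP, report the between-group ratio of change with its CI as supporting evidence.

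The cost is one SAP paragraph, matching wording in the objective, and one margin decision. No new samples are needed. The downside is that a claim of no interaction becomes harder to make: the subset with a pre-PrEP baseline is smaller than the full group, and a tight margin may need more pairs than are available. At 0.20 SD, for example, 215 pairs would be needed against an upper bound of 196. In that case the estimation wording is the workable option.
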